6.4.3 Dose Limiting Toxicity Definition

A DLT defined as any of the following events, which occur during the 21-day DLT evaluation period of Part 1, except those that are clearly due to underlying disease or extraneous causes:

A **hematologic** DLT is defined as:

- Grade 4 anemia
- Grade 3 anemia requiring transfusion
- Grade 4 neutropenia lasting > 7 days
- Febrile neutropenia
- Grade 4 thrombocytopenia
- Grade 3 thrombocytopenia which results in clinically significant bleeding or requires a transfusion

A **non-hematologic** DLT is defined as:

- Hy's law case - AST and/or ALT $\geq 3 \times$ ULN and bilirubin $\geq 2 \times$ ULN, and without initial findings of cholestasis (serum alkaline phosphatase [ALP] activity $< 2 \times$ ULN) and no other reason that could explain the combination of increased transaminases and serum total bilirubin
- Any other non-hematologic toxicity \geq Grade 3 with the exception of the following:
 - Grade 3 fatigue for ≤ 7 days.
 - Grade 3 nausea, vomiting, or diarrhea in the absence of premedication that responds to therapy and improves by at least 1 grade within 3 days or to \leq Grade 1 within 7 days.
 - Grade 3 elevations of ALP and GGT elevations, unless considered clinically relevant by the Investigator.
 - Grade 3 elevation of serum lipase or serum amylase for ≤ 7 days if without clinical signs or symptoms of pancreatitis.
 - Grade 3 electrolyte abnormalities that normalize within 48 hours (with or without medical intervention) and that do not manifest themselves clinically; in such instance, a follow-up sample MUST be taken within 48 hours to check whether such normalization has occurred.

- In addition, the following will be considered DLTs:
 - Grade 2 noninfectious pneumonitis that does not resolve to \leq Grade 1 within 3 days of the initiation of maximal supportive care
 - Any grade of immune-mediated rash with bullous formation
 - Grade 2 or 3 immune-mediated peripheral neuromotor syndrome (such as Guillain-Barre and myasthenia gravis) that does not resolve to Grade \leq 1 within 30 days or that exhibits signs of respiratory insufficiency or autonomic instability
 - Grade 2 immune-mediated myocarditis that does not resolve to Grade \leq 1 within 3 days of initiating optimal medical management, including systemic corticosteroids
 - Grade 2 or 3 immune-mediated myositis/polymyositis that does not resolve to Grade \leq 1 within 30 days of initiating optimal medical management, including systemic corticosteroids, or that exhibits signs of respiratory insufficiency regardless of optimal medical management
 - Immune-mediated increase in creatinine $>3 \times$ ULN, or $>3 \times$ baseline for patients with a baseline creatinine elevated above ULN

Patients who experience a DLT that resolves or stabilizes with appropriate medical management may continue treatment at the discretion of the Investigator in consultation with the Sponsor.

6.4.4 Dose Escalation Steering Committee

A Dose Escalation Steering Committee (DESC) will oversee dose escalation and general safety of the study.

Membership of the DESC will include:

- Medical and/or pharmacovigilance representative(s) from the Sponsor and/or designee
- Investigator(s) from each participating site

The DESC will be responsible for:

- Determining dose levels to be administered and the MTD based on assessment of safety findings and DLTs.
- Monitor the safety of the study and review its progress at monthly intervals or more frequently as required.

Decisions made at DESC meetings will be documented in written minutes, which will be distributed to DESC members.

6.5 Dose Delays and Modifications

6.5.1 Loncastuximab Tesirine

If a patient experiences any Grade ≥ 3 (≥ 2 for edema, effusion, or increased AST/ALT/GGT) toxicity, loncastuximab tesirine must be held until the toxicity resolves to Grade 1 or less (Grade 1 or baseline for peripheral neuropathy). If loncastuximab tesirine dosing is delayed by more than 3 weeks and the toxicity is considered at least possibly related to loncastuximab tesirine, then subsequent doses of loncastuximab tesirine will be reduced by 50%.

In addition, the Investigator may reduce the dose of loncastuximab tesirine by 50% for any Grade ≥ 3 (≥ 2 for edema, effusion, or increased AST/ALT/GGT) toxicity that is possibly related to loncastuximab tesirine but does not result in dosing delay of more than 3 weeks if they feel it is in the best interest of the patients.

6.5.2 Durvalumab

If a patient experiences any Grade ≥ 3 toxicity, durvalumab must be held until the toxicity resolves to Grade 1 or less (Grade 1 or baseline for peripheral neuropathy).

In addition, durvalumab must be held for the following Grade ≥ 2 specific immune-mediated toxicities:

- Pneumonitis/ILD
- Diarrhea/Colitis
- Hepatitis (elevated liver function tests)
- Nephritis or renal dysfunction
- Persistent rash (>1 -2 weeks)
- Endocrinopathy (except isolated hypothyroidism or Type 1 diabetes mellitus)
- Neurotoxicity
- Peripheral neuromotor syndromes
- Myocarditis
- Myositis/polymyositis

See [Section 13.3](#), [Appendix 3](#) for guidelines regarding management and resumption of durvalumab therapy after specific immune-mediated toxicities.

For all other toxicities, durvalumab must be held until the toxicity resolves to Grade 1 or less (Grade 1 or baseline for peripheral neuropathy).

Durvalumab will be given at full dose when resumed after being held for toxicity, i.e., there will be no dose reduction.

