7.1 Discontinuation from Study Treatment

A patient may be discontinued from study treatment for any of the following reasons:

- Disease progression
- Unacceptable toxicity
- Patient decision
- Major protocol deviation
- The Investigator determines that it is in the best interest of the patient to discontinue the patient's participation in the study
- Discontinuation of the study by the Sponsor
- Pregnancy
- Death

IMPORTANT: Study treatment discontinuation is not to be automatically considered as withdrawal from the study. Patients discontinuing study treatment will be asked to perform an EOT visit ([Section 4.4](#)) and continue with the Follow-up period ([Section 4.5](#)) as per protocol.

The investigational site should make every effort to complete follow-up per protocol. If patients are unable to return to the site, patient status, including but not limited to survival status, may be obtained by site staff via phone, email, or mail.

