* A score of 3 in many patients indicates a good prognosis with standard treatment, especially if at the time of an interim scan. However, in trials involving PET where de-escalation is investigated, it may be preferable to consider a score of 3 as inadequate response (to avoid undertreatment). Measured dominant lesions: Up to six of the largest dominant nodes, nodal masses, and extranodal lesions selected to be clearly measurable in two diameters. Nodes should preferably be from disparate regions of the body and should include, where applicable, mediastinal and retroperitoneal areas. Non-nodal lesions include those in solid organs (e.g., liver, spleen, kidneys, lungs), GI involvement, cutaneous lesions, or those noted on palpation. Nonmeasured lesions: Any disease not selected as measured, dominant disease and truly assessable disease should be considered not measured. These sites include any nodes, nodal masses, and extranodal sites not selected as dominant or measurable or that do not meet the requirements for measurability but are still considered abnormal, as well as truly assessable disease, which is any site of suspected disease that would be difficult to follow quantitatively with measurement, including pleural effusions, ascites, bone lesions, leptomeningeal disease, abdominal masses, and other lesions that cannot be confirmed and followed by imaging. In Waldeyer's ring or in extranodal sites (e.g., GI tract, liver, bone marrow), FDG uptake may be greater than in the mediastinum with complete metabolic response, but should be no higher than surrounding normal physiologic uptake (e.g., with marrow activation as a result of chemotherapy or myeloid growth factors).

** PET 5PS: 1, no uptake above background; 2, uptake \leq mediastinum; 3, uptake $>$ mediastinum but \leq liver; 4, uptake moderately $>$ liver; 5, uptake markedly higher than liver and/or new lesions; X, new areas of uptake unlikely to be related to lymphoma.

[Cheson et al., 2014](#)

13.3 Appendix 3 Guidelines for Durvalumab Dose Modification for Specific Immune-mediated Reactions

| Adverse Events | Severity grade of the Event (NCI CTCAE version 4.03) | Dose modifications | Toxicity management |
|---|--|--|--|

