| Grade 3 or 4 | 
For Grade 3 or 4:
 
Permanently discontinue study drug/study regimen.
 | 
For Grade 3 or 4:
 
 – Manage severe infusion-related reactions per institutional standards (e.g., IM epinephrine, followed by IV diphenhydramine and ranitidine, and IV glucocorticoid). |

CTCAE Common Terminology Criteria for Adverse Events; IM intramuscular; IV intravenous; NCI National Cancer Institute.

Non-Immune-Mediated Reactions

| Severity Grade of the Event (NCI CTCAE version 4.03) | Dose Modifications | Toxicity Management |
|--|---|---|
| Any Grade | Note: Dose modifications are not required for AEs not deemed to be related to study treatment (i.e., events due to underlying disease) or for laboratory abnormalities not deemed to be clinically significant. | Treat accordingly, as per institutional standard. |
| Grade 1 | No dose modifications. | Treat accordingly, as per institutional standard. |
| Grade 2 | Hold study drug/study regimen until resolution to \leq Grade 1 or baseline. | Treat accordingly, as per institutional standard. |
| Grade 3 | Hold study drug/study regimen until resolution to \leq Grade 1 or baseline. For AEs that downgrade to \leq Grade 2 within 7 days or resolve to \leq Grade 1 or baseline within 14 days, resume study drug/study regimen administration. Otherwise, discontinue study drug/study regimen. | Treat accordingly, as per institutional standard. |
| Grade 4 | Discontinue study drug/study regimen (Note: For Grade 4 labs, decision to discontinue should be based on accompanying clinical signs/symptoms, the Investigator's clinical judgment, and consultation with the Sponsor.). | Treat accordingly, as per institutional standard. |

Note: As applicable, for early phase studies, the following sentence may be added: "Any event greater than or equal to Grade 2, please discuss with Study Physician."

AE Adverse event; CTCAE Common Terminology Criteria for Adverse Events; NCI National Cancer Institute.

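### Section 6.5.2 neither states nor points to the Appendix 3 durvalumab stop rules for infusion-related and non-immune-mediated reactions

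*Protocol*

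**What the plan says.** Section 6.5.2 of the protocol is the operative durvalumab rule. It opens with a hold for any toxicity of Grade 3 or higher until Grade 1 or less, then lists immune-mediated toxicities that require a hold from Grade 2. It cites Appendix 3 "for guidelines regarding management and resumption of durvalumab therapy after specific immune-mediated toxicities". The next sentence covers the remainder: "For all other toxicities, durvalumab must be held until the toxicity resolves to Grade 1 or less". The section ends: "Durvalumab will be given at full dose when resumed after being held for toxicity, i.e., there will be no dose reduction".

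Appendix 3 (Section 13.3) is titled "Guidelines for Durvalumab Dose Modification for Specific Immune-mediated Reactions". After the organ-specific immune tables it has two further tables that the title does not name.

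- Infusion-related reactions, Grade 3 or 4: "Permanently discontinue study drug/study regimen".
- Non-immune-mediated reactions, Grade 4: "Discontinue study drug/study regimen (Note: For Grade 4 labs, decision to discontinue should be based on accompanying clinical signs/symptoms", together with the Investigator's judgment and Sponsor consultation.
- Non-immune-mediated reactions, Grade 3: hold to Grade 1 or baseline. Dosing resumes if the event is down to Grade 2 within 7 days, or to "Grade 1 or baseline within 14 days, resume study drug/study regimen administration. Otherwise, discontinue study drug/study regimen".

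The non-immune table exempts events judged unrelated to treatment and laboratory abnormalities judged not clinically significant.

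Section 7.1 is permissive: "A patient may be discontinued from study treatment for any of the following reasons". Unacceptable toxicity is on its list, without grades.

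**The concern.** Infusion-related and non-immune reactions fall within the remainder for which Section 6.5.2 states its own rule. By limiting the reference to Appendix 3 and then covering everything else with a hold, the section steers a reader away from the two tables that contain the stop rules. The appendix title does the same. Nothing says which text prevails.

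The event is foreseeable: Section 1.2.4 lists infusion-related and hypersensitivity reactions among the risks of durvalumab. What is at stake is a full-dose re-challenge in a patient whom Appendix 3 would take off the drug.

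**Working it through.** The plan gives no figure to reproduce. The check sets the rules side by side and then uses the dosing calendar to see when the difference would matter.

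| Event | Section 6.5.2 | Appendix 3 |
|---|---|---|
| Grade 3–4 infusion-related reaction | Hold to Grade ≤1; full dose if resumed | Permanent stop |
| Grade 4 non-immune event | Hold to Grade ≤1; full dose if resumed | Stop; judgment and Sponsor consultation for laboratory values |
| Grade 3 non-immune event, neither Grade ≤2 by day 7 nor Grade ≤1/baseline by day 14 | Hold, no time limit | Stop |

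**Calendar** (Sections 4.3 and 6.3.2; Cycle 1 is 21 days, Cycle 2 is 42 days):

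- Dose 1: Cycle 1 Day 8 = day 8.
- Dose 2: Cycle 2 Day 15 = 21 + 15 = day 36.
- Dose 3: Cycle 3 Day 1 = 21 + 42 + 1 = day 64.
- Interval: 36 − 8 = 28 days and 64 − 36 = 28 days.

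**Infusion reaction.** If the reaction is back to Grade 1 or less within 28 days (an assumption; the documents give no durations), the hold ends before the next dose is due and withholds nothing. Appendix 3 would have ended durvalumab.

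**Grade 3 non-immune event.** Count days from onset and suppose the event starts just after a dose. If it is still Grade 3 on day 7 and first reaches Grade 1 between days 15 and 28, it misses the 14-day limit but precedes the next dose. That window is 28 − 14 = 14 days long. Section 6.5.2 costs the patient no dose; Appendix 3 discontinues.

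**Reach of the DLT clause.** A Grade 3 or higher infusion-related reaction in the DLT period of Part 1 meets the non-hematologic DLT definition in Section 6.4.3 unless it is clearly due to disease or an extraneous cause. Continuing then requires Sponsor consultation. The period ends on day 8 + 21 = day 29. Dose 2 is due on day 36, or day 36 − 2 = day 34 at the earliest with the visit window. The clause therefore covers reactions to the first dose in Part 1, not to later Part 1 doses or any Part 2 dose. Even where it applies, it requires consultation and not a stop.

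**The case against.** The strongest reply is that the two sections do not contradict each other. Section 6.5.2 never orders resumption: its full-dose sentence is conditional and only rules out a reduced dose. A hold is a minimum step, Appendix 3 adds a stricter one, and a site that stops obeys both. The stop rules are in the protocol, in an appendix that sites must already use for durvalumab. This stands. A reader might infer that Section 6.5.2 instructs sites to re-dose after a severe infusion reaction; it does not.

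Oversight is also wider than the DLT clause. Section 4.3 ends treatment at unacceptable toxicity. Section 6.4.4 has the Dose Escalation Steering Committee review safety at least monthly. Section 8.2.2 requires serious events to reach the Sponsor's pharmacovigilance group within 24 hours, and a life-threatening reaction is serious by definition. This also stands, so it would be wrong to infer that such patients are unprotected. But none of these provisions is a stop rule for the named events.

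The non-immune Grade 3 row has a workable reading: its first sentence sets when dosing may restart, and the second sets which events qualify. That answers most of the charge of ambiguity. It does not remove the difference from Section 6.5.2, which has no time limit.

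Finally, SAP Section 3.3 records that the trial ended early and that only Part 1 data will be analyzed. This limits the practical reach, especially for Part 2, but does not correct the text.

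**Conclusion.** The point holds as a gap in wording and cross-reference that bears on patient safety. Section 6.5.2 gives a hold-only rule for three kinds of event that Appendix 3 resolves by stopping, and no precedence is stated. A site working from Section 6.5.2 alone could give a full-dose re-challenge. It should be corrected, but it is not a design failure.

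No event rate can be attached, because the documents report neither the frequency nor the duration of these reactions on the combination. The conclusion rests on the text, and for infusion reactions on the assumption that some settle within the 28-day interval. A reader might count the doses left in the year after a first reaction and treat that as the harm. It is only a calendar ceiling: progression, clinical judgment and the safeguards above would often end treatment sooner.

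A reader might also infer that the Appendix 3 stops extend to loncastuximab tesirine. The appendix title and Section 6.5.2 both tie them to durvalumab, and Section 6.5.1 gives loncastuximab its own rule.

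The effect on the analysis is negligible. The dose-interruption endpoint is descriptive and the SAP tests no hypothesis.

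**What to change.** 1. In Section 6.5.2, qualify both the opening Grade 3 or higher sentence and the sentence on all other toxicities with: *except that durvalumab is permanently discontinued after a Grade 3–4 infusion-related reaction, and non-immune-mediated events are managed, including discontinuation, as specified in Appendix 3*.
2. Widen the Section 6.5.2 cross-reference and the Appendix 3 title so that both name the infusion-related and non-immune-mediated tables.
3. Have the clinical team confirm one resume threshold for the non-immune Grade 3 row.

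Items 1 and 2 are wording only. They give force to rules already in Appendix 3 and leave its exemptions and its judgment clause for Grade 4 laboratory values intact. Item 3 needs one clinical decision. No patients, visits or data are added, and the SAP does not change.

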6.6 Overdose Management

An overdose is any dose of study drug(s) given to a patient that exceeds the dose described in the protocol. Any overdose, with or without associated AEs, must be promptly reported to the Sponsor. There are no data available to determine what the effects of overdose of loncastuximab tesirine are and whether they can be reversed. There is no specific experience in the management of durvalumab overdose in patients. Symptomatic treatment and standard supportive care measures for the management of any observed toxicity should be applied.

6.7 Premedication and Supportive Care

6.7.1 Premedication

Unless contraindicated, administer dexamethasone 4 mg PO or IV twice daily:

- the day before each loncastuximab tesirine administration (if possible),
- the day of loncastuximab tesirine administration (first dose at least 2 hours prior to administration when not given the day before; otherwise any time prior to administration), and
- the day after loncastuximab tesirine administration.

Patients who experience an infusion-related hypersensitivity reaction will receive the alternative premedication regimen specified in [Section 6.7.3](#).

6.7.2 Treatment of Edema and Pleural Effusion

Peripheral edema and serosal effusions (pleural and pericardial effusions, ascites) have been seen in patients receiving loncastuximab tesirine. Patients should be advised to monitor their weight on a daily basis (preferably each morning around the same time) and notify the study site of weight gain greater than 1 kg from baseline.

Patients with weight gain greater than 1 kg from baseline, new or worsening edema, and/or new or worsening pleural effusion, pericardial effusion, or ascites, should be treated with spironolactone at standard doses. The dose of spironolactone may be titrated as clinically indicated. Additional diuretic support may be added if there is further increase in weight, edema, or effusion.

6.7.3 Treatment and Prophylaxis of Infusion-related Hypersensitivity Reactions

Medications for the treatment of severe hypersensitivity reactions, including anaphylaxis, should be available for immediate use and may be administered according to institutional standard of care.

Any patient who experiences an infusion-related hypersensitivity reaction should receive prophylactic treatment in subsequent cycles according to the guidelines below or as per institutional standard of care:

- On Day 1 of each cycle, patients should receive dexamethasone 20 mg PO or IV 12 and 6 hours before the start of the loncastuximab tesirine infusion. When necessary, 12 and 6 hours before the first infusion may be defined as “immediately before sleeping” and “immediately after waking up.”
- On Day 1 of each cycle, patients will be given diphenhydramine hydrochloride 50 mg IV 30 minutes before the start of the loncastuximab tesirine infusion.
- On Day 1 of each cycle, patients will be given ranitidine (or equivalent) 50 mg IV 30 minutes before the start of the loncastuximab tesirine infusion.
- For 2 days following administration of loncastuximab tesirine on Day 1, patients are to take dexamethasone 4 mg PO or IV twice daily (BID).

6.7.4 Skin Rash

Skin rash has been reported with loncastuximab tesirine, as well as with another investigational agent containing the same PBD warhead ([Rudin et al., 2017](#)). The rash has been reported in areas at risk for sun exposure; it is therefore recommended that precautions are taken to avoid prolonged exposure of skin to sunlight.

6.7.5 Other Supportive Care

- Although the study patient population has a low risk for development of tumor lysis syndrome (TLS) compared to patients with acute disease ([Cairo et al., 2010](#)), patients should be observed for development of TLS and treated according to site standard treatment protocols.
- As testing in animals showed testicular toxicity (atrophy with reduced spermatogenesis), male patients are advised to consider cryopreservation of sperm prior to treatment with loncastuximab tesirine, where applicable.

6.7.6 Concomitant Medications and Procedures

Medications (except for the study drugs) and procedures will be recorded in the eCRF starting from the ICF signature date or from 14 days prior to C1D1, whichever is earlier, and continuing until 30 days after last dose of study drug.

6.7.7 Permitted During Study

All medications or procedures for the clinical care of the patient, including management of AEs, are permitted during the study, except for those listed in [Section 6.7.8](#).

Hematopoietic growth factors are permitted as per American Society of Clinical Oncology guidelines ([Smith et al., 2006](#)).

6.7.8 Prohibited During Study

- Other anticancer therapy with the exception of hormonal therapy for maintenance treatment of breast and prostate cancer.
- Other investigational agents.
- Live vaccines including for 30 days after the last dose of durvalumab.
- Current or prior use of immunosuppressive medication within 14 days before the first dose of durvalumab. The following are exceptions to this criterion:
 - Intranasal, inhaled, topical steroids, or local steroid injections (e.g., intra-articular injection)
 - Systemic corticosteroids at physiologic doses not to exceed 10 mg/day of prednisone or its equivalent
 - Steroids as premedication for hypersensitivity reactions (e.g., computed tomography [CT] scan premedication)

7 Discontinuation

The reason for discontinuation and the date of discontinuation will be collected for all patients.

Note: Once discontinued from the study for any reason, patients are not permitted to be re-enrolled.

